### **Primary aims 1-3: weight loss at 24 months and leading up to 24 months**

Weight loss at 24 months will be compared between PCMH vs FFS and DM vs FFS, as well as DM vs PCMH. Hierarchical linear mixed models will be used to examine the group differences, accounting for the correlation between patients from the same clinic.

We will fit a hierarchical linear mixed model with longitudinal weight change at 6, 18, and 24 months study visits. This model will account for the correlation between patients in the same clinic as well as correlation of measures from the same patient. In secondary analysis, percent weight loss will also be compared across the three groups using the same approach. Clinical cutpoints of 5% and 10% will be compared across arms at 6 and 24 months using generalized linear mixed models. The analytical plans may be adapted to provide the best approach using the latest methodological advancements.

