# **II. RESEARCH PLAN AND DESIGN**

## **A. Study Objectives**

**Research Goal:** To advance our knowledge of obesity treatment in rural primary care by directly comparing the effectiveness of two alternative models of care with the current standard of care. If the hypotheses are correct, the results may warrant a new standard of care for obesity treatment in rural primary care practices.

**Study Aims:** The primary aims of the study are to test the hypotheses that both the PCMH model (with in clinic group visits) and DM model (with group phone visits) are more effective than the currently reimbursed FFS model (with in clinic individual visits) in reducing weight at 24 months.

[figure not shown]
The secondary aims of the study are to 1) test the hypothesis that the DM is more effective than the PCMH model in reducing weight at 24 months, 2) to compare the effects of the three arms on patient-centered outcomes (i.e. blood pressure, fasting glucose and lipids, quality of life, sleep, and stress), 3) to assess the heterogeneity of treatment effects across demographic subgroups (i.e. race/ethnicity, education level, income level, employment status, and distance traveled/travel time to receive care), and 4) to evaluate the reach and sustainability of the three arms following the RE-AIM evaluation framework.

**Statement of Purpose:** The purpose of this study is to test the comparative effectiveness of three viable treatment models for addressing obesity in rural primary care.

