### **C3. Power calculation and sample size**

A total of 36 practices with 40 participants per practice will be enrolled in the study (1440 participants total). Twelve practices (480 participants total) will be enrolled in each arm (FFS, PCMH, DM). A net treatment effect of 2.75 kg is supported by the available literature and our previous work. Treatment effects for PCP counseling alone with varying levels of intervention intensity have ranged from 0.1 to 1.7 kg at 12 to 24 months follow-up with the majority falling below 1 kg. For this pragmatic trial conducted in underserved rural areas, we expect the FFS treatment effect to fall in the lower end of this range. Team-based care approaches with obesity counseling delivered by auxiliary staff (PCMH) have ranged from 2.9 to 5.1 kg at 24 mo. In an entirely remote disease management program, Appel et al. reported weight loss of 4.6 kg at 24 mo. Our remote group phone-based program currently being delivered outside the primary care setting has shown 10.2 kg loss at 18 mo in preliminary analyses. We expect this to be lower in a pragmatic primary care trial, however a net effect  $\geq 2.75$  kg is achievable. To determine sample size, we set the type I error at 0.025 (overall type I error rate of 0.05 for first two aims), intraclass correlation coefficient at 0.05, and 40 patients/clinic. With 36 clinics, the trial will have 80% power to detect a net treatment effect of 2.75 kg (SD = 8).

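### One analysis heading calls DM vs PCMH primary, the rest of the plan makes it secondary, and no alpha or testing order is given for it (minor)

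*Combined protocol and SAP*

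**What the plan says.** Section I.A2 (Aims and hypotheses) lists two primary aims, PCMH vs FFS and DM vs FFS, both on weight at 24 months. It puts DM vs PCMH third, under the secondary aims. Section II.A (Study Objectives) repeats this: "The secondary aims of the study are to 1) test the hypothesis that the DM is more effective than the PCMH model".

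Section II.C1 heads the weight analysis "Primary aims 1-3: weight loss at 24 months and leading up to 24 months". The text beneath names the three pairwise contrasts and one hierarchical mixed-model approach. It gives no alpha and no order of testing. The headings that follow begin at secondary aim 4.

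Section II.C3 supplies the only alpha statement: "we set the type I error at 0.025 (overall type I error rate of 0.05 for first two aims". The design behind it is 36 practices of 40 patients, split equally over the three arms. Its power statement reads: "With 36 clinics, the trial will have 80% power to detect a net treatment effect of 2.75 kg (SD = 8".

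**The concern.** Section V.A refers the reader to II.C for the statistical procedures, so the heading in II.C1 sits in the text the analysts will use. That heading sorts the aims into primary and secondary differently from I.A2 and II.A.

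DM vs PCMH is not an incidental contrast. It is a directional hypothesis on the primary endpoint (I.A2), and V.B says DM is expected to do better. Yet the plan does not say whether Aim 3 is tested at 0.025, at 0.05, only after Aims 1 and 2, or reported as an estimate. II.C1 also lets the analysis plan be adapted, so the choice could be made after the results are known. At stake is whether a DM vs PCMH result could be reported as a primary finding with no alpha allotted to it.

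**Working it through.** **1. Side by side.**

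| Place | Status of DM vs PCMH |
|---|---|
| I.A2 | secondary (Aim 3) |
| II.A | secondary |
| II.C1 heading | primary |
| II.C3 | outside the alpha split, which covers the first two aims |

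Three places agree and one heading differs.

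**2. Reproduce the plan's figures.** Inputs from II.C3: 12 practices per arm, 40 patients per practice, ICC 0.05, SD 8, difference 2.75 kg, alpha 0.025 per test. Sidedness is not stated, so I assume two-sided tests and normal statistics.

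- Alpha for Aims 1 and 2: 0.025 + 0.025 = 0.05, as stated.
- Design effect: 1 + (40 − 1) × 0.05 = 2.95. Effective n per arm: 480 / 2.95 = 162.7.
- SE of a contrast: 8 × √(2 / 162.7) = 0.887 kg. Standardised effect: 2.75 / 0.887 = 3.10.
- Power: Φ(3.10 − 2.241) = 80.5%, against the stated 80%.
- Required n: 161 × 2.95 = 475 per arm, against 480.
- One-sided 0.025 would give 87.3%, so two-sided is the reading that fits.

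**3. Familywise error under the global null.** With equal arms, the two contrasts against FFS have correlation 0.5, and the DM vs PCMH statistic is the difference of those two z statistics. By simulation:

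| Family | Bonferroni bound | Simulated error |
|---|---|---|
| Aims 1 and 2 at 0.025 (the plan) | 0.050 | 0.046 |
| Aims 1 to 3, all at 0.025 (assumed) | 0.075 | 0.064 |
| Aims 1 and 2 at 0.025, Aim 3 at 0.05 (assumed) | 0.100 | 0.085 |
| Aims 1 to 3 at 0.05 / 3 = 0.0167 | 0.050 | 0.044 |

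The second and third rows rest on an alpha for Aim 3 that the plan does not give. The last row is what three co-primary tests would need with an equal Bonferroni split. Power per contrast would then be 76.0% instead of 80.5% with the same 36 × 40.

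**4. Holm on Aims 1 and 2.** Test the smaller p at 0.025; if it is rejected, test the other at 0.05. A contrast is rejected if |z| > 2.241, or if |z| > 1.960 and the other contrast has |z| > 2.241.

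For the 80% retention floor in II.C1, take 32 completers per practice. The design effect is 1 + 31 × 0.05 = 2.55, effective n is 384 / 2.55 = 150.6, and SE is 0.922.

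| True effects | Fixed 0.025 each | Holm |
|---|---|---|
| Both 2.75 kg, per contrast, full data | 80.5% | 85.0% |
| Both 2.75 kg, per contrast, 80% retained | 77.1% | 81.9% |
| Both 2.75 kg, win both, full data | 69.4% | 78.4% |
| One 2.75 kg and one zero, the effective arm, full data | 80.5% | 80.6% |

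Holm rejects everything that the fixed split rejects, and it keeps familywise error at or below 0.05.

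**The case against.** A reader might infer from the heading that the plan's overall 0.05 fails. The documents do not support that. II.C3 limits the figure to the first two aims, and for those it is correct; nowhere does the plan claim 0.05 across three tests. Under the two-aim family there is no excess primary error.

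The heading also has an innocent explanation. Aims 1 to 3 share one outcome and one model, so they share a paragraph, and the sentence beneath adds DM vs PCMH after the two FFS contrasts. II.C3 stands in the same section II.C, so an analyst who follows II.C also meets the two-aim limit. This explanation is an inference, but it fits the other three places.

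Holm corrects no error. A Bonferroni split over two primary tests is valid and matches the stated power, and the gain from Holm depends on both arms working. Gating Aim 3 on both primary rejections is a trade-off, because a stated hypothesis would lose its formal test whenever either FFS contrast failed.

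All of this stands. It leaves the contradictory heading and the absence of any rule for Aim 3.

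**Conclusion.** This is a minor inconsistency with a real gap behind it. The II.C1 heading conflicts with I.A2 and II.A on the status of DM vs PCMH, and no section gives that contrast an alpha, a place in a testing order or estimate-only status. The weight of the text makes Aim 3 secondary. On that reading the stated 0.05 and 80% power both stand.

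The figures 0.064 and 0.085 apply only if Aim 3 is counted as primary, at an assumed 0.025 or 0.05, with equal arms and under the global null. They show what the heading would imply if followed; they are not the error rate of the plan.

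The Holm gain (80.5% to 85.0% per contrast, 69.4% to 78.4% for both) assumes two-sided tests, normal statistics, full data and a true effect of 2.75 kg in both arms. With 12 practices per arm, a t reference would lower the absolute power: the fixed 0.025 test has 75.2% on 22 degrees of freedom and 77.0% on 33.

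**What to change.** 1. Retitle the II.C1 section *Primary aims 1-2 and secondary aim 3*, to agree with I.A2, II.A and II.C3.
2. Add a sentence saying that Aim 3 lies outside the primary alpha and is reported as a secondary result with a confidence interval. If the sponsor wants a formal test, it can instead be made at 0.05 only after both primary contrasts are rejected. That order keeps familywise error at or below 0.05, but gives up the formal test when either primary contrast fails.
3. State that the tests are two-sided.
4. As an improvement, test Aims 1 and 2 by Holm instead of at a fixed 0.025 each.

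If the sponsor does intend three co-primary contrasts, alpha and power must be reset; an equal Bonferroni split gives 0.0167 per test and 76.0% power.

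The cost is a few sentences, with no change to sample size or data collection. One consequence of Holm should be noted: a contrast rejected at the second step can have a 97.5% interval that includes zero, so the text should say which interval is reported. All of this should be fixed before the outcome data are analysed.

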#### ***Disease Management Arm (DM), Phone Group Visits***

As with the PCMH arm, the DM model will deliver a group-based comprehensive lifestyle intervention. Sessions in the DM condition will be delivered in groups via conference call by obesity treatment specialists, employed at KUMC, with Masters' degrees in nutrition, exercise science, public health or psychology. Our preliminary research has shown that group phone counseling is more effective compared to individual phone counseling (also R18 HL122720). We have found this delivery approach to be especially ideal for rural residents, because it eliminates travel burden, and also because it provides social support while preserving a level of anonymity. In the DM delivery model, groups will be formed across multiple practices and regions of the Midwest. Calls will occur approximately at 6:30am, 12:00pm, 5:30 pm, or 7:00pm on Monday, Tuesday, Thursday or Friday which has been the most universally available time and avoids conflicts related to Wednesday evening church activities common in our rural communities. Group norms are established early on regarding active participation, no multi-tasking, maintaining a supportive tone, and attendance and punctuality. All group members participate up to their comfort level, providing support and strategies for one another. Counselors encourage group cohesiveness and facilitate participants interacting directly with one another. Participants are encouraged to submit personal bio-sheets with a picture for sharing with the group. Counselors set expectations for participants to treat sessions as a standing appointment. Counselors will document session attendance and patient notes in REDCap.

***Integration with primary care.*** Obesity treatment specialists will send periodic progress reports to the patients' PCP at the practice. Timing of the reports will be based on group start dates and subsequent study milestones. The first report will be sent after 3-months of counseling participation; the remainder of the reports will be sent on or around the time of the follow-up data collection visits and survey completion—specifically at 6, 12, 18 and 24 months.

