#### E5. Timeline (Figure 3)

The original funding period for this study was 5 years, January 1, 2015 to December 31, 2019. A global contract modification fully executed in February 2018 extended the period of performance through April 30, 2020. The final timeline is included in Figure 3. All project milestones, as required by PCORI, will be completed within this time frame. The study will be implemented in three cohorts, with 12 primary care practices in each cohort (4 in each of the 3 arms). Patient recruitment will begin in January 2016 for cohort 1, June 2016 for cohort 2 and September 2016 for cohort 3. Practices in the PCMH and DM arms will enroll 40 patients over a 6 month time period. The FFS arm will enroll 40 patients over a 9 month period (indicated in the timeline below with dotted lines). Each patient in all arms will be followed for 2 years. Analysis and dissemination of the primary outcomes will happen in the final 6 months of the project period.

Figure 3. Study Timeline

	Year 1 - 2015				Year 2 - 2016				Year 3 - 2017				Year 4 - 2018				Year 5 - 2019				Year 6 - 2020	
	Q1	Q2	Q3	Q4	Q1	Q2	Q3	Q4	Q1	Q2	Q3	Q4	Q1	Q2	Q3	Q4	Q1	Q2	Q3	Q4	Q1	Q2
Cohort 1	Study Preparation IRB Approval Practice Recruitment DSMB Charter Obesity Trainings			Practice Training	Recruitment		Phase 1		Phase 2										Analysis and Dissemination			
Cohort 2					Practice Training	Recruitment		Phase 1		Phase 2												
Cohort 3						Practice Training	Recruitment		Phase 1		Phase 2											

Figure 4. Study Flow

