#### **I2. Study activities**

Centralized mail and phone-based patient recruitment and screening will occur at KUMC (see Section III). Provider trainings will be delivered both centrally and locally within the practices with collaboration and uniformity across all three institutions. Tracking of provider training completion will be managed by KUMC study personnel. Patient consent, in-person assessment visits, and FFS and PCMH counseling visits will occur within the primary care practices; these procedures will be the same across practices affiliated with KUMC, UNMC, and Marshfield Clinic. Some data collection visits may be conducted at a patient's home, or another location convenient for the patient, if they are unable to come to the primary care practice for the visit. Counseling visits for the DM arm will be conducted by KUMC study personnel for all 12 practices randomized to this arm. KUMC study personnel will also handle (for all 36 practices and 1440 patients) centralized distribution of self-report questionnaires (on-line and by mail) and related data entry, tracking of patient recruitment and retention rates, retention phone calls to patients who miss assessment visits and have not been reached by the practice, and reporting requirements for KUMC IRB and PCORI.

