## **D. Procedures to Protect Participant Confidentiality**

Identifiable information will be required on the physician clearance form, hardcopy consent forms, which, and hardcopy data collection forms at some sites that are not entering directly into REDCap, will be collected by practice staff and held in a secure location until they are mailed/faxed to, or picked up by KUMC research staff. After the KUMC study team receives the physician clearance forms, consent forms, and all source documents they will be kept in a locked file cabinet.

Attendance sheets may be printed and used for note taking during group meetings in the PCMH and DM arms. Attendance sheets will include the each participant's study ID, first name, session attendance, and notes. After each meeting, the group leader will enter all attendance info and notes into REDCap and will store hardcopies in a locked file cabinet.

Participants in the PCMH and DM arms will be given the option to complete a biosheet including a family or individual photo, name, and questions about their hometown, family, and hobbies. Group members will submit their biosheet to their group leader via mail or email after the first week of the intervention. Group leaders will compile and send biosheets to all group members. Once biosheets are sent to the group members, the group leader will keep a password protected PDF in the KUMC server and will store all hardcopies in a locked file cabinet. The biosheet activity is voluntary for all participants.

Participants will be informed that sharing of all information is voluntary both during assessment visits and counseling sessions. They will be encouraged to share concerns regarding weight-related issues with the clinic and study staff only to the extent that they feel comfortable. Respect for confidentiality during group visits will be highlighted as a group norm at the outset and reinforced throughout the intervention period.

Participants in the DM and PCMH arms have the option to create Lose It! accounts. Participants will enter an email address and user name when they set up their account. Counselors in the PCMH and DM arms will have access to group member's Lose It! data for the purposes of giving dietary feedback. Lose It! account set up and use will be voluntary and confidential information will be discussed in the consent form. The texting option will also be voluntary and will be discussed in the consent form.

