Group phone meetings will be recorded through Arkadin and written notes for each counseling session may be taken by the counselor. The audio recordings will be downloaded by the counselor and saved on the KUMC secure network. Recordings will be labeled with the date of the recording and a de-identified group number. There will be no identifying participant information included in the recording labels. Information concerning these recordings will be discussed in the consent form.

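### The primary model has no term for DM call groups, which cut across clinics, so call-group correlation is missing from the DM-FFS and DM-PCMH standard errors; the effect is small and depends on assumptions

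*Combined protocol and SAP*

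**What the plan says.** Section II.C1 (Primary aims 1-3) specifies a hierarchical linear mixed model for weight change at 6, 18 and 24 months and names two sources of correlation: "This model will account for the correlation between patients in the same clinic as well as correlation of measures from the same patient". It adds that the analysis may be adapted to newer methods, but names no further clustering level. Section II.C3 sizes the trial with one clustering parameter, "intraclass correlation coefficient at 0.05".

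Section II.E2c describes how DM is delivered: "In the DM delivery model, groups will be formed across multiple practices and regions of the Midwest". It also says: "Counselors encourage group cohesiveness and facilitate participants interacting directly with one another". Section II.I2 adds: "Counseling visits for the DM arm will be conducted by KUMC study personnel for all 12 practices randomized to this arm". Section II.E5 places four DM practices in each of three cohorts. PCMH groups, by contrast, are run by each practice for its own patients (II.B and II.E2c), and FFS visits are individual.

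No section gives the size or number of DM call groups, a group ICC, or the number of DM counselors.

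**The concern.** In DM, call group is crossed with clinic. Two patients of different clinics on the same calls share a counselor, a peer group and a course of sessions, and peer support is an intended part of the treatment. A clinic random effect cannot represent correlation between those two patients. When groups are mixed across clinics, the clinic-only model treats group variance almost entirely as independent patient-level noise.

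The treatment estimate is not biased; only its precision is in question. Aim 2 is one of two primary tests at 0.025, and Aim 3 uses the same DM mean. If call-group correlation exists and clinic correlation is similar in all arms, these intervals are somewhat too narrow and the p-values somewhat too small. Aim 1 needs no group term, because PCMH groups are nested in the clinic and the clinic effect absorbs their correlation.

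**Working it through.** **Inputs from the plan (II.C3).** SD 8 (variance 64), 12 clinics x 40 = 480 patients per arm, clinic ICC 0.05, type I error 0.025 per comparison, difference 2.75 kg.

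**Assumed.** Groups of 15 (range 10 to 20), so G = 480/15 = 32 groups; group ICC r of 0.01 to 0.05; total variance held at 64; groups mixed at random over clinics.

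**1. The plan's power.** Design effect 1 + 39 x 0.05 = 2.95. Effective n per arm 480/2.95 = 162.7. SE = 8 x sqrt(2/162.7) = 0.887 kg. With two-sided 0.025 (z = 2.2414), power = Phi(2.75/0.887 - 2.2414) = 0.805. The stated 80% reproduces. Sidedness is not stated; one-sided 0.025 would give 0.873.

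**2. Add call groups, clinic ICC 0.05 in every arm.** FFS mean variance = 64 x (0.05/12 + 0.95/480) = 0.3933. DM mean variance = 0.3933 + 64 x r x (1/32 - 1/480), while the clinic-only model still sees 0.3933. Actual error = 2 x [1 - Phi(2.2414 x 0.887/true SE)]; power of a valid test = Phi(2.75/true SE - 2.2414).

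| Group ICC | DM variance | True SE | Model SE too small by | Error | Power of a valid test |
|---|---|---|---|---|---|
| 0.01 | 0.4120 | 0.897 | 1.2% | 0.027 | 0.795 |
| 0.02 | 0.4307 | 0.908 | 2.3% | 0.0285 | 0.785 |
| 0.05 | 0.4867 | 0.938 | 5.5% | 0.034 | 0.755 |

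Over group sizes 10 to 20 and group ICC 0.01 to 0.05, the shortfall is 0.8 to 7.2% and the error 0.026 to 0.038. At 80% retention (384 per arm), groups of 15 and ICC 0.02 to 0.05, the model SE is 0.922 against a true 0.942 to 0.970: 2.1 to 5.0% too small, error 0.028 to 0.033.

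**3. Groups formed only within a cohort.** Clinic-mates then share a group more often than chance over the whole arm, so the clinic effect picks up a little of the group correlation. The model SE rises only to 0.889-0.893, and the error is 0.028 to 0.033 for group ICC 0.02 to 0.05.

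**4. Simulation.** REML, 12,000 trials per setting, Monte Carlo SE about 0.0014, Welch degrees of freedom as a stand-in for Satterthwaite. Error without and with the group term:
- no group effect: 0.024 and 0.023;
- group ICC 0.02: 0.027 and 0.023;
- group ICC 0.05: 0.031 and 0.022;
- groups within cohort, ICC 0.02: 0.025 and 0.022;
- groups within cohort, ICC 0.05: 0.029 and 0.021.

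A separate simulation on clinic means (20,000 trials, groups of 16 within cohort) gave 0.025, 0.027 and 0.033 at group ICC 0.01, 0.02 and 0.05 without the term.

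**5. Lower clinic correlation in DM, one pooled clinic variance.** Take DM clinic ICC 0.02 and group ICC 0.02, with FFS and PCMH at 0.05.
- Clinic-mean variances: FFS and PCMH 64 x (0.05 + 0.95/40) = 4.72; DM as the model sees it 64 x (0.02 + 0.98/40) = 2.848.
- Pooled: (2 x 4.72 + 2.848)/3 = 4.096, so model SE = sqrt(4.096 x 2/12) = 0.826.
- True SE = sqrt(4.72/12 + 2.848/12 + 0.0373) = 0.817.

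The model SE is now about 1% too large and the error is 0.0235. Other cases by the same formula: DM clinic ICC 0.01 with group ICC 0.01 to 0.02 gives 0.020 to 0.022; 0.03 with 0.02 gives 0.0253; 0 with 0.05 gives 0.0258; 0.01 with 0.05 gives 0.028. If clinic variance is estimated separately by arm there is no offset: 0.029 to 0.039 over DM clinic ICC 0 to 0.03 and group ICC 0.02 to 0.05.

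**The case against.** - **The size is all assumption.** This stands. At group ICC 0.02 the simulated error of 0.027 is barely distinguishable from 0.024 with no group effect, and with groups formed within a cohort it is 0.025. Clear inflation needs a group ICC near 0.05 or above, for which the documents give no evidence.
- **The direction is not settled.** A reader might infer that the DM standard errors are necessarily too small. The documents do not support that. DM care is delivered centrally, so a lower DM clinic ICC is plausible. The plan mentions no arm-specific clinic variance, so a single pooled one is the ordinary reading. Step 5 shows that the planned test can then be about right or slightly conservative.
- **The group term can over-correct.** DM calls are offered at several times of day, and random assignment to groups is not stated. If patients sort by availability, members may resemble each other without influencing each other. Simulated sorting on a prognostic trait gave an apparent group ICC of about 0.01 to 0.06 while the DM arm-mean variance stayed near its theoretical 0.393. A group intercept would read this as cluster variance. This stands as a real cost.
- **Counselor variance remains.** With four counselors at ICC 0.02 (both assumed), simulated error is 0.056 without the group term and 0.051 with it. This stands, but it matters only if inference is meant to reach beyond the KUMC team actually used.
- **The simulations are simplified.** They omit the repeated measures and the stratification. This is fair, and is a reason to read the figures as orders of magnitude.
- **The plan permits adaptation and nothing contradicts itself.** True, but the clause names no remedy. A group term added after the data are seen could move the Aim 2 p-value and would be open to criticism as post hoc.

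**Conclusion.** The omission is real: the planned model cannot represent correlation within DM call groups, and this touches Aims 2 and 3 but not Aim 1. The consequence is modest and conditional. With clinic ICC 0.05 in every arm, groups of 15 and group ICC 0.02 to 0.05, the DM-FFS standard error is 2.3 to 5.5% too small and the error is about 0.027 to 0.034 against 0.025 (lower end from simulation, upper end from the closed form). At group ICC 0.01, or at 0.02 with groups formed within a cohort, simulation shows almost no effect. With lower DM clinic correlation and a pooled clinic variance, the error can fall to about 0.020 to 0.025.

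A reader might also infer that the stated 80% power is wrong. It is not: it reproduces at 80.5% on its own inputs, which simply include no call-group correlation. This is an inexpensive improvement to the analysis plan.

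**What to change.** Before outcomes are compared by arm, add to the primary model a random intercept for the DM call group as first assigned. Apply it in the DM arm only, crossed with clinic, with Satterthwaite or Kenward-Roger degrees of freedom. Keep it whatever its estimated variance, so that the choice is not data-driven. PCMH needs no group term.

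Confirm that each DM patient can be linked to a call group. Section IV.D says "Recordings will be labeled with the date of the recording and a de-identified group number" and, on attendance, "After each meeting, the group leader will enter all attendance info and notes into REDCap", but no section says that group ID is a REDCap field.

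Report the clinic-only model alongside. Prespecify two sensitivity analyses: clinic variance allowed to differ by arm, and DM counselor as a further effect, which requires counselor identity. State that the group term does not cover counselor variance.

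**Cost.** A few lines of text, one variance component and a data-linkage check. With no within-group similarity, the DM-FFS standard error widens by about 1% (simulated mean 0.877 to 0.885; power about 0.805 to 0.798). If similarity comes only from sorting by call time, the widening could reach roughly 2 to 6% at an apparent group ICC of 0.02 to 0.05 (0.908/0.887 = 1.02; 0.938/0.887 = 1.06), with no gain in validity; adjusting for baseline prognostic covariates may reduce this. The variance components rest on few clusters: 12 DM clinics and, at the assumed sizes, 24 to 48 call groups.
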